7.3.2 Demographics and Baseline Characteristics

Frequency distributions and summary statistics for demographic and baseline variables will be presented by treatment group and for all subjects combined for all treated subjects. Demographic variables to be summarized include: age, gender, race, and geographic region. See Table 7.3-1 for countries in each region.

Table 7.3-1: Demographics and Baseline Characteristics

Region	Country
North America	Canada and United States
Europe	Czech Republic, France, Germany, Greece, Italy, Netherlands, Poland, Spain, and United Kingdom
Latin America	Argentina

Baseline variables to be summarized include the following:

- Physical measurements (height, body weight, body mass index)
- Vital signs (systolic blood pressure, diastolic blood pressure, and heart rate)
- Disease characteristics
 - New York Heart Association Class prior to admission
 - Ejection fraction (%)
 - Heart failure etiology (as collected in the CRF Heart Failure Etiology page at screening)
 - Number of heart failure hospitalizations in past year
 - Time since original HF diagnosis to first treatment of study drug
 - Time since first diuretic use in the current episode of decompensation to first treatment of study drug
 - Comorbidities listed in “Specific Disease History” CRF page, including but not limited to coronary artery disease, hypertension, diabetes, and presence of atrial fibrillation
- Important laboratory variables (including NT-proBNP, serum sodium and eGFR)
- Current heart failure medications

Start time of first diuretic use will be obtained from “Previous and Concomitant Intravenous Medications” CRF page.

Current heart failure medications will be taken from CRF previous and concomitant IV and non-IV medications pages with Use of “Heart Failure” and start date prior to first treatment of study drug. The CRF pages collect IV medications administered starting from one week prior to randomization.

7.3.3 Physical Measurements

Physical measurements such as body weight and height will be summarized by nominal visit for all treated subjects, as overall and by treatment. Measurements will also be listed for all treated subjects.

7.3.4 Medical History and Previous Medications

Medical history and previous medications taken prior to dosing will be listed for all treated subjects.

7.4 Extent of Exposure

Study drug administration and randomization schedule will be documented as per subject listings.

Any non-study medications taken by subjects, any conducted non-study medical treatment procedures, and any utilized non-study diagnostic procedures will also be listed.

Percentage of subjects with discontinuation due to symptomatic hypotension, as well as percentage of subjects with down-titrations or discontinuations as a result of low blood pressure, either protocol specified clinically relevant hypotension, or asymptomatic decreases will be analyzed and presented in the same manner as the primary endpoint.

The final infusion dose at the completion of 48 hours infusion will be summarized descriptively by treatment. The subjects who discontinue prematurely from infusion will be counted as having a final infusion dose of 0 µg/kg/min. Subjects who are down-titrated and complete the 48 hours infusion will be counted as having a final infusion dose of 1/2 of the scheduled dose at time of down-titration. For example, the final dose will be 3 µg/kg/min if down-titration occurs when 6 µg/kg/min is administered for a subject in Part I (Cohort 1) and the subject otherwise complete dosing after the down-titration.

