4.5 Selection and Timing of Dose for Each Subject

Subjects will be administered study medication as a continuous IV infusion over 48 hours.

Body weight measured at screening will be used for dose calculations.

Every effort must be made to initiate study drug administration promptly after randomization.

See Pharmacy Manual for additional dosing information.

4.5.1 Dose Reductions, Temporary Interruptions, and Permanent Discontinuations of Study Drug Due to Blood Pressure

Any decision to lower the dosage level of study drug or discontinue study drug should be based on the Investigators assessment of the subject's overall clinical stability, in the context of appropriate ongoing monitoring of the subject's condition. A 50% dosage adjustment downward maybe be achieved by decreasing the rate of study drug infusion.

In Part I (Cohort 1) subjects who require a dose reduction or temporary interruption during the first infusion period, hours 0 to 4 (dose of 3 µg/kg/min), will be permanently discontinued from study drug.

Study drug infusion rate may be reduced by 50%, temporarily interrupted, or permanently discontinued. See [Figure 4.5.1-1](#) and the following sections for more detail.

Dose Reduction:

- If the subject experiences SBP < 95 mm Hg, without symptoms related to hypotension, the measurement must be repeated within 15 minutes. If the SBP remains < 95 mm Hg, the dose reduction must occur
- A 50% dosage adjustment downward may be achieved by decreasing the rate of study drug infusion by half
- After a dose reduction, the dose cannot be increased again

Temporary interruption:

- If the systolic blood pressure reduces below < 85 mm Hg, and remains < 85 mm Hg during a repeated measure within 15 minutes, the study drug must be interrupted for at least 1 hour
- For subjects that report symptoms consistent with hypotension (eg, dizziness, lightheadedness, etc.), and are related to hypotension, study drug must be interrupted for at least 1 hour

[figure not shown]
Resuming Study Drug

- Study drug may be resumed at 50% of the dose after 1 hour interruption, if SBP rises to values ≥ 105 mm Hg and any symptoms of hypotension, if present, have resolved.
- If after 4 hours, the subject’s SBP remains below < 105 mm Hg, or if symptoms persist, then study drug must be permanently discontinued
- After a dose reduction, the dose cannot be increased again

Permanent discontinuation of the infusion:

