8.4.3 Safety Analyses

Troponin T will be summarized descriptively by treatment for each time point, as well as change from baseline.

Percentage of subjects who have died (all- cause and CV related) will be summarized descriptively by treatment.

All recorded adverse events will be listed and tabulated by system organ class, preferred term and treatment. Vital signs and clinical laboratory test results will be listed and summarized by treatment. Any significant physical examination findings, and clinical laboratory results will be listed. ECG readings will be evaluated by the investigator and abnormalities, if present, will be listed.

Percentage of subjects with discontinuations due to symptomatic hypotension, as well as percentage of subjects with down-titrations or interruptions or discontinuations as a result of hypotension, either protocol specified clinically relevant hypotension, or asymptomatic decreases will be summarized descriptively by treatment.

In addition, the final infusion dose at the completion of 48 hours infusion will be summarized descriptively by treatment. The subjects who discontinued prematurely from infusion would be counted as having a final infusion dose of 0 µg/kg/min.

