3.3 Safety

Safety objectives include the following:

- Evaluate the effect of BMS-986231 on the incidence of symptomatic hypotension
- Evaluate the effect of BMS-986231 on the incidence of SBP < 90 mm Hg

- Evaluate the incidence of dose reductions, temporary interruptions, and permanent discontinuation of BMS-98623 infusions
- Evaluate the safety and tolerability of a continuous 48-hour infusion of BMS-986231 in hospitalized HFrEF subjects with ADHF
- Evaluate the effect of BMS-986231 on high sensitivity (Hs) Troponin T
- Assess the effect of BMS-986231 on mortality at Day 182

[REDACTED]

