4.2.2 Other Safety Endpoints

Other safety endpoints include the following:

- The incidence of symptomatic hypotension up to 6 hours after the end of study drug infusion
- The incidence of SBP < 90 mm Hg (confirmed by a repeated value, see Section 8.1) up to 6 hours after the end of study drug infusion
- Change in Troponin T from baseline to Hour 24, 48, and 72
- Percentage of subjects who have died (all- cause and CV(cardiovascular) related) through Day 182

Additionally, the percentage of subjects with discontinuation due to symptomatic hypotension, as well as percentage of subjects with down-titrations, interruptions or discontinuations as a result of low blood pressure, either protocol specified clinically relevant hypotension, or asymptomatic decreases will be assessed. Other safety endpoints include the incidence of Adverse Events and Marked Laboratory Abnormalities, changes from baseline in vital signs, ECGs, physical measurements and laboratory assessments through Hour 120 or discharge, whichever comes first. The incidence of Serious Adverse Events will be assessed though Day 32.

[REDACTED]

maximally tolerated dose approximately 50-70%, based on detecting an increase of 3-fold or 2.5-fold in incidence, and using sample decision rules that are consistent with above. Also, the design will provide an option to select a titrated 12 µg/kg/min dose approximately 60% of the time when that dose is tolerated, but a non-titrated 12 µg/kg/min dose is not tolerated. Conversely, the study design will not identify a maximally tolerated dose is established from Part II (Cohort 2) approximately 80%-85% of the time when no maximally tolerated dose exists.

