Subjects counted in the endpoint “Percentage of subjects with down-titrations, interruptions or discontinuations as a result of low blood pressure, either protocol specified clinically relevant hypotension, or asymptomatic decreases” are those who have ‘Hypotension’ as the reason for rate reduction, infusion interruption or discontinuation.

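### SAP 7.4 leaves temporary interruptions out of the low-blood-pressure dose-modification analysis, contradicting the endpoint as defined in SAP 4.2.2 and 8.1 and protocol 8.3.4 and 8.4.3

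*SAP*

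**What the plan says.** SAP 7.4 (Extent of Exposure) says that the "percentage of subjects with down-titrations or discontinuations as a result of low blood pressure" will be analysed and presented like the primary endpoint. Under SAP 7.6.1 that means event rates, risk differences and relative risks with exact 95% confidence intervals.

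Elsewhere the endpoint has three components. SAP 4.2.2 lists the "percentage of subjects with down-titrations, interruptions or discontinuations as a result of low blood pressure". SAP 8.1 counts a subject when hypotension is recorded "as the reason for rate reduction, infusion interruption or discontinuation". Protocol 8.4.3 summarises the "percentage of subjects with down-titrations or interruptions or discontinuations as a result of hypotension", and protocol 8.3.4 defines the endpoint with the same three actions. A safety objective in SAP 3.3 is also explicit: "Evaluate the incidence of dose reductions, temporary interruptions, and permanent discontinuation".

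SAP 7.4 also sets the final infusion dose. Premature discontinuation scores 0 µg/kg/min. For down-titration the rule reads: "Subjects who are down-titrated and complete the 48 hours infusion will be counted as having a final infusion dose of 1/2 of the scheduled dose", taken at the time of down-titration. It has no sentence on subjects who were interrupted and then resumed. Protocol 4.5.1 gives the dose for them: "Study drug may be resumed at 50% of the dose after 1 hour interruption", subject to blood pressure recovery and resolution of symptoms.

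**The concern.** The trial is meant to identify doses that are tolerated with regard to hypotension, so how often the infusion had to be altered for low blood pressure is direct evidence. SAP 7.4 is the only SAP section that states how this endpoint is analysed, and it omits one of the three components without giving a reason.

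The omitted component is the response to the more marked event. Under protocol 4.5.1, a rate reduction follows a confirmed SBP below 95 mm Hg without symptoms. Interruption applies when SBP "remains < 85 mm Hg during a repeated measure within 15 minutes, the study drug must be interrupted for at least 1 hour", and also when the subject has symptoms related to hypotension. Two programmers, one following 7.4 and the other following 8.1, could produce different tolerability percentages from the same data.

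**Working it through.** **Components side by side**

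| Source | Reduction | Interruption | Discontinuation |
|---|---|---|---|
| SAP 7.4 (analysis) | yes | no | yes |
| SAP 4.2.2 (definition) | yes | yes | yes |
| SAP 8.1 (counting rule) | yes | yes | yes |
| Protocol 8.3.4 and 8.4.3 | yes | yes | yes |

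The SAP says it is based on revised protocol 01, which is not among the documents. The two protocol versions that are available (02 and 02c) agree with each other here.

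**Who could be missed**

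Trace an interrupted subject through protocol 3.5 and 4.5.1:

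1. SBP not recovered, or symptoms persisting, after 4 hours: permanently discontinued, so counted in 7.4.
2. Resumed, and hypotension or its symptoms recur: permanently discontinued, so counted.
3. Already down-titrated before meeting the interruption criterion: permanently discontinued, so counted.
4. Part I, hours 0 to 4: permanently discontinued, so counted.
5. Interrupted once, resumed at 50%, infusion completed: counted in 7.4 only if the resumption is also recorded as a rate reduction.

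Only group 5 is exposed, and only where interruption is the sole record.

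**Size per subject**

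Formula: shortfall in percentage points = 100 × k / n, where k is the number of such subjects in the arm and n the arm size. Protocol 8.1 plans about 70 per group in Part II and 50 in Part I.

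- Part II, k = 1: 100 × 1/70 = 1.4 points.
- Part I, k = 1: 100 × 1/50 = 2 points.

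The documents give no value for k. As an assumption for scale only, k = 4, 7 or 14 of 70 gives 5.7, 10 or 20 points.

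**Final dose**

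The SAP's own example is a Part I subject down-titrated while receiving 6 µg/kg/min: 1/2 × 6 = 3 µg/kg/min, which reproduces. Applying the protocol's 50% resumption to a Part II subject in group 5 gives 1/2 × 12 = 6 or 1/2 × 6 = 3 µg/kg/min. SAP 7.4 does not say that this value is used, and it does not assign another. SAP 7.3.1 names interruption and down-titration separately, but only to say that both count as completing treatment if the subject does not stop permanently.

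**The case against.** The strongest reply is that the SAP as a whole keeps interruptions. Sections 4.2.2 and 8.1 both name them, and 8.1 holds the operational counting rule, so 7.4 may be a drafting slip that a programmer would resolve in favour of 8.1. That is fair, and it makes this an inconsistency located in 7.4. It does not remove the inconsistency, because 7.4 is where the analysis is stated.

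Resumption at half rate might also be entered as a rate reduction, in which case nobody is missed. The case report form is not available, so this can be neither confirmed nor excluded; the point is conditional on it.

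Information on interruptions is not lost altogether. SAP 7.11 lists them among the inputs to the Part II dose decision, and study drug administration is listed by subject. The events that trigger interruption are also ones the primary endpoint is built to count. These facts limit the consequence, but they do not supply the between-arm estimates and intervals that 7.4 promises for this endpoint.

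On final dose, 7.4 opens by referring to the dose at completion of the infusion, and protocol 4.5.1 repeats, in its text on resuming, that a reduced dose cannot be raised again. Resumption at 50% can therefore be read as a down-titration. That reading is reasonable, so the final-dose issue is a gap in wording.

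**Conclusion.** SAP 7.4 contradicts the endpoint definition and counting rule elsewhere in the SAP and in the protocol, and should be corrected. The error is 1.4 percentage points per affected subject in an arm of 70 and 2 points in an arm of 50. It applies only to subjects interrupted for low blood pressure, resumed, and completing with no other qualifying record. Their number is unknown, and the 4 to 14 of 70 used above is an assumption. The primary endpoint rests on blood pressure and symptom records and is unaffected.

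Three stronger readings are tempting and not supported:

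- **Interrupted-and-resumed subjects are counted at full dose.** No passage says so. If they were, k = 4 to 14 of 70 (assumed) would raise the mean final dose of the 12 µg/kg/min arm by k × 6/70 = 0.34 to 1.20 µg/kg/min, but this describes one possible reading of a silent rule.
- **The half-dose formula fails in Part I when an interruption spans the Hour 8 step from 6 to 12 µg/kg/min.** The text is ambiguous there, and no failure is shown.
- **The shortfall can be measured against the 3% and 4% differences in the sample decision rules of protocol 8.1.** Those rules concern clinically relevant hypotension, not dose modification.

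**What to change.** In SAP 7.4, name all three actions (down-titrations, interruptions and discontinuations) and refer to the SAP 8.1 counting rule, so that one definition serves both sections.

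As a secondary clarification, state that for subjects interrupted and then resumed the final-dose summary uses the infusion rate actually recorded at the end of infusion. Say separately how a subject whose infusion is paused at Hour 48 is handled, and reconcile that with SAP 7.3.1: scoring such a subject 0 would use the value that 7.4 reserves for premature discontinuation, while 7.3.1 treats interrupted subjects who do not stop permanently as completers.

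The cost is SAP wording and the matching table programs. SAP 8.1 already relies on recorded reasons for each of the three actions, so counting interruptions needs no new data. Whether the rate at the end of infusion is captured directly should be checked against the case report form. No dosing rule changes.

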7.5 Efficacy

7.5.1 Primary Efficacy Analysis

There is no primary efficacy analysis for this study. The primary safety analysis is discussed in [Section 7.6.1](#).

7.5.2 Secondary Efficacy Analysis

NT-proBNP will be summarized descriptively for all treated subjects by treatment for each time point, as well as change from baseline. Geometric mean and coefficient of variation (%CV) will also be presented for the original values and percent of baseline.

The NRS is an ordinal scale of 0 to 10. A score of 0 represents “I am not breathless at all” and 10 represents “I am the most breathless I can possibly imagine”.

To incorporate the correlations among NRS assessments at different time points and an appropriate representation of effect of baseline assessments, the change from baseline at time point t (Hour 24, 48, and 72) in NRS assessments will be analyzed using a longitudinal repeated measures method. The model will include treatment, region and time as fixed effects and baseline value as covariate. Furthermore, interaction terms of time by treatment, time by region and time by baseline value will be included. An unstructured variance-covariance matrix for the NRS assessments within same subject will be used (Autoregressive structure will be used if the model does not converge with unstructured matrix.). The SAS[®] procedure PROC MIXED will be used.

After obtaining the estimates of mean change from baseline at time point t in NRS assessments, the mean change in AUC within a treatment group or difference in mean change in AUC between treatment groups will be estimated within the framework of the mixed model, using the formula based on the Trapezoidal rule:

$$\Delta AUC = \sum_{i=1}^3 (t_{i+1} - t_i) \frac{y_{t_{i+1}} + y_{t_i}}{2}$$

where y_{t_i} is the estimate of mean change from baseline at target time t_i in a treatment group for estimation of mean change in AUC within treatment group, and for estimation of difference in change in AUC between treatment groups, y_{t_i} is the estimate of mean difference between treatment groups in change from baseline at target time t_i . The variability of ΔAUC will also be estimated

within the framework of the mixed model in SAS using variability from terms used in the ESTIMATE statement.

Missing values for the dyspnea NRS will only be imputed if a NRS cannot be obtained because the subject has died or is physically unable to complete the form. In these cases, a worst score (i.e. 10) imputation will be used for that time point. Missing values for subjects who are discharged prior to Hour 120 will not be imputed.

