8.4.2.2 Secondary Endpoint Analyses

NT-proBNP will be summarized descriptively by treatment for each time point, as well as change from baseline.

Analyses for changes from baseline in the resting dyspnea as measured by the 11-point NRS will be done using a longitudinal repeated measures model, with baseline value and region as covariates. A trapezoidal rule will be applied to calculate AUC using model-estimated values from the time points. Missing values for the dyspnea NRS will not be imputed, except if a NRS cannot be obtained because the subject has died or is physically unable to complete the form. In these cases, a worst score imputation will be used for that time point.

[REDACTED]

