3.2 Secondary

Secondary objectives include the following:

- Assess the effect of BMS-986231 on NT-proBNP
- Assess the effect of BMS-986231 on patient-reported resting dyspnea as measured by the 11-point Numerical Rating Scale (NRS)

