4.1.2 Secondary Efficacy Endpoints

Secondary endpoints include the following:

- Change in NT-proBNP from baseline to Hour 24, 48, 72, 120 or discharge (whichever comes first), and at Day 32
- Change in patient-reported resting dyspnea from baseline through Hour 72, as measured by the area under the curve (AUC) of the 11-point Numerical Rating Scale (NRS) obtained at baseline, and Hours 6, 12, 24, 48, and 72

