7.1 General Methods

Results from Part I (Cohort 1) and Part II (Cohort 2) will be presented separately, unless otherwise noted.

Except as noted otherwise, descriptive summaries will be presented for continuous variables using number of subjects (N), mean, standard deviation (SD), median, minimum and maximum. Descriptive summaries for categorical variables will utilize counts and percentages. Several analyses noted in subsequent sections will present 95% confidence intervals (CIs), but no pre-specified significance testing will be included.

Adverse events and medical history will be coded according to the most recent Medical Dictionary for Regulatory Activities (MedDRA) version. Previous and concomitant medications will be coded using the WHO Drug Dictionary.

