7.6.2.4 Clinical Laboratory Evaluations

The results of all protocol-specified clinical laboratory tests will be listed. Scheduled laboratory measurements and corresponding change from baseline values will be summarized by treatment and scheduled time points for each laboratory test.

The criteria used for classifying laboratory test results as markedly abnormal will be listed.

Laboratory results for subjects with any marked laboratory abnormality (scheduled and unscheduled) will be listed. This listing will include all observations for the specific laboratory test and subject, not only the marked laboratory abnormalities. The frequency of subjects with any marked laboratory abnormality as well as hematology, serum chemistry, and urinalysis marked abnormalities, based on pre-specified criteria (see Table 7.6.2.4-1), will be presented.

Troponin T will be summarized descriptively by treatment for each time point, as well as change from baseline. Geometric mean and coefficient of variation (%CV) will also be presented for the original values and percent of baseline.

Table 7.6.2.4-1: Laboratory MA Criteria

Parameter	Test Code	Direction of Change	MA Criteria in US Standard Units (apply to labs collected after baseline only)	MA Criteria in SI Units (apply to labs collected after baseline only)
HEMATOLOGY				
Hemoglobin	HB	Low only	> 2 g/dl decrease compared to pre-dose or Value ≤ 8 g/dl	> 20 g/l decrease compared to pre-dose or Value ≤ 80 g/l
Hematocrit	HCT	Low only	< 0.75 × pre-dose	< 0.75 × pre-dose
Erythrocytes	RBC	Low only	< 0.75 × pre-dose	< 0.75 × pre-dose
Platelet Count	PLAT	Low Only	< 100,000/mm ³ (or < 100× 10 ⁹ cells/L)	< 100× 10 ⁹ cells/L
Leukocytes	WBC	Low/High	< 0.75 × LLN or > 1.25 × ULN, or if pre-dose < LLN then use < 0.8 × pre-dose or > ULN if pre-dose > ULN then use > 1.2 × pre-dose or < LLN	< 0.75 × LLN or > 1.25 × ULN, or if pre-dose < LLN then use < 0.8 × pre-dose or > ULN if pre-dose > ULN then use > 1.2 × pre-dose or < LLN
Neutrophils (absolute)	NEUTA	Low Only	< 1.0 × 10 ³ cells/μL	< 1.0 × 10 ⁹ cells/L
LIVER/KIDNEY				
Alkaline Phosphatase	ALP	High only	> 2 × ULN	> 2 × ULN
Aspartate Aminotransferase	AST	High only	> 3 × ULN, > 5 × ULN, > 10 × ULN	> 3 × ULN, > 5 × ULN, > 10 × ULN
Alanine Aminotransferase	ALT	High only	> 3 × ULN, > 5 × ULN, > 10 × ULN	> 3 × ULN, > 5 × ULN, > 10 × ULN
Bilirubin, Total	TBILI	High only	> 2 × ULN	> 2 × ULN

Table 7.6.2.4-1: Laboratory MA Criteria

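### NT-proBNP, one of two secondary endpoints, has no planned adjusted contrast with placebo in the visible SAP, and the laboratory windows give patients discharged before Hour 96 no value at its Hour 120 or discharge time point

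*SAP*

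**What the plan says.** The secondary objective in SAP 3.2 is "Assess the effect of BMS-986231 on NT-proBNP". SAP 4.1.2 defines the endpoint as "Change in NT-proBNP from baseline to Hour 24, 48, 72, 120 or discharge (whichever comes first), and at Day 32". For the analysis, SAP 7.5.2 states that "NT-proBNP will be summarized descriptively for all treated subjects by treatment for each time point, as well as change from baseline" and that "Geometric mean and coefficient of variation (%CV) will also be presented for the original values and percent of baseline". Protocol 8.4.2.2 gives the same descriptive plan: "NT-proBNP will be summarized descriptively by treatment for each time point, as well as change from baseline".

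The other secondary endpoint, the dyspnea NRS, is handled in the same SAP section by a longitudinal model: "The model will include treatment, region and time as fixed effects and baseline value as covariate". Differences between treatment groups are estimated from that model, with their variability. On inference in general, SAP 7.1 says: "Several analyses noted in subsequent sections will present 95% confidence intervals (CIs), but no pre-specified significance testing will be included".

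For timing, SAP Table 8.3-2 assigns laboratory values by hours since the start of infusion. Hour 72 covers Hour 60 to before Hour 96, and Hour 120 covers Hours 96 to 132. There is no row for discharge or for Day 32. Protocol Table 5.1-2 schedules NT-proBNP at Hours 24, 48 and 72 and at a combined Hour 120/discharge visit, with no draw at Hour 96. Its footnote c drops the repeat at discharge if the assessment was done in the previous 12 hours.

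**The concern.** An objective about effect calls for a comparison with placebo and a statement of its precision. In the visible plan the NRS gets one, adjusted for baseline and for the region used to stratify randomization. Likert responses (SAP 7.7.1), worsening heart failure and renal function (7.7.2), deaths (7.6.2.1) and rehospitalizations (7.10) are all presented like the primary endpoint, that is, with 95% CIs against placebo. NT-proBNP ranks above these as a listed secondary endpoint but gets by-arm summaries only.

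The second issue is that the endpoint and the window table do not describe the same patients. The endpoint gives an early-discharged patient a value at discharge. The table gives that patient a value at this time point only if the draw was at Hour 96 or later. The Hour 120 row would then cover a subset that the endpoint does not define. The recommended minimum stay ends at about Hour 72, so the discharges concerned are within the protocol.

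**Working it through.** **Starting point.** The plan states no figure for NT-proBNP. Its only sizing figures concern hypotension. The Part II ones reproduce by exact enumeration (81.7% and 79.7% against the stated 82% and 80%, reading the fold condition as strictly greater), but they do not bear on this point.

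**Windows.** Inputs are the draw schedule and 12-hour footnote (Protocol Table 5.1-2), the recommended stay of 48 + 24 = 72 hours (Protocol 5.1.2), SAP Table 8.3-2, and the closest-value rule (SAP 8.4).

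| Discharge at | Draw available | Row in Table 8.3-2 | Value at Hour 120 |
|---|---|---|---|
| Before Hour 72 | Last scheduled or discharge draw | Hour 48 or Hour 72 | None |
| Hours 72–84 | Hour 72 draw, not repeated (72 + 12 = 84) | Hour 72 | None |
| After 84, before 96 | Hour 72 draw and a separate discharge draw | Hour 72 for both | None |
| Hours 96–120 | Discharge draw | Hour 120 | Present |

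- Hour 72 has a ±2 hour allowance, so the 84-hour boundary can lie anywhere from 70 + 12 = 82 to 74 + 12 = 86.
- In the third row the Hour 72 draw is within 2 hours of target and the discharge draw about 12 hours or more away, so the discharge draw is set aside.
- The laboratory rule in SAP 8.4 works in days and cannot separate two draws on one date. Whichever value it picks, the Hour 120 row stays empty.

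**Day 32.** 32 × 24 = Hour 768, and ±2 days gives Hours 720 to 816, which matches no laboratory row. The SAP 8.3 rule that uses the Day 32 value regardless of time stands in the vital-signs paragraph. After the Hour 120/discharge visit, however, only one NT-proBNP draw is scheduled, so there is nothing to choose between.

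**Precision of an adjusted contrast (illustration).** The SD *s* of log NT-proBNP and its correlation *ρ* with baseline are assumptions, and data are taken as complete. SE = √(2s²(1 − ρ²)/n); the 95% CI is the ratio ×/÷ exp(1.96 × SE). For s = 0.7, ρ = 0.8, n = 70: SE = √(2 × 0.49 × 0.36/70) = 0.0710, giving exp(0.139) = 1.149.

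| s, ρ | n = 70 (Part II) | n = 50 (Part I) |
|---|---|---|
| 0.7, 0.8 | 1.149 | 1.179 |
| 0.7, 0.5 | 1.222 | 1.268 |
| 1.0, 0.8 | 1.220 | 1.265 |
| 1.0, 0.5 | 1.332 | 1.404 |

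With equal SD at both times, the log change has SD s√(2(1 − ρ)). The adjusted half-width is then √((1 + ρ)/2) of the unadjusted one on the log scale: √0.90 = 0.949 at ρ = 0.8 and √0.75 = 0.866 at ρ = 0.5. Adjustment therefore narrows the interval by about 5% to 13%.

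**The case against.** The strongest reply is that the descriptive plan is deliberate. Protocol and SAP agree, the trial has no primary efficacy endpoint, and no significance testing is planned. Troponin T has a similarly worded objective and the same treatment: "Troponin T will be summarized descriptively by treatment for each time point, as well as change from baseline". The primary endpoint itself has no stated region adjustment, and the SAP promises the variability of the NRS contrast without naming a 95% CI for it. All of this stands. It shows that the plan is consistent, so this is a gap against the objective and not a contradiction. It does not argue against an interval, since SAP 7.1 rules out tests and allows CIs.

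A reader might go further in several ways that the documents do not support:
- *The tables carry no information on uncertainty.* N, mean and SD by arm yield a crude interval for the difference in mean change. A crude interval for the ratio also follows if the %CV is the geometric one. What is missing is a displayed, adjusted contrast.
- *Any interval would be chosen after seeing the data.* SAP 7.9 and Protocol 8.4.5 cannot be read, and the Data Presentation Plan is not supplied.
- *Early discharge biases the Hour 120 comparison.* That would need discharge timing to differ by arm and to be related to NT-proBNP. The documents give no figure for either.
- *Day 32 is undefined.* It is one visit with one draw; only a table row is missing.
- *Dose selection is affected.* NT-proBNP is not named among the Part I dose criteria in SAP 7.11.

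Assigning values by clock time also has a merit: it does not pool different sampling times. That is a real cost of the discharge visit proposed below.

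**Conclusion.** The point holds in two parts. First, the visible SAP gives a listed secondary endpoint with an effect objective no displayed or adjusted contrast with placebo, although a standard one needs only data already collected. Second, Table 8.3-2 does not deliver the endpoint as defined: patients discharged before Hour 96 have no value at the Hour 120 or discharge time point, while discharge draws from Hour 96 on are captured. The second part follows from the documents' own schedule and windows and rests on no assumed figure.

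The size of either effect cannot be stated from the documents, because the share discharged before Hour 96 and the variability of NT-proBNP are not given. The interval factors of 1.15 to 1.33 (70 per arm) and 1.18 to 1.40 (50 per arm) show only what the added analysis could resolve under assumed inputs; they do not measure harm from the present plan. The change is worth making but does not touch the primary safety conclusion.

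**What to change.** 1. In SAP 7.5.2 keep the descriptive tables and add a repeated measures model on log NT-proBNP at Hours 24, 48, 72, 120 and Day 32. Include treatment, time, region, log baseline and their interactions with time, with unstructured covariance. Report ratios of geometric means versus placebo with 95% CIs and no significance test. If the model does not converge, fall back on heterogeneous compound symmetry. The autoregressive fallback used for the NRS ignores the unequal spacing. Spatial power implies almost no correlation across the last gap: Hour 120 to Hour 768 is 27 intervals of 24 hours, and an assumed 24-hour correlation of 0.8 gives 0.8^27, about 0.002.
2. In SAP 8.3 add a derived Hour 120 or discharge laboratory visit. For patients discharged before Hour 120 it takes the discharge sample, or the last draw in the previous 12 hours if none was repeated. Name it as the result for the endpoint as defined, with fixed-time Hour 120 as the sensitivity result. Show actual sampling times by arm, because the derived visit mixes times. State that a draw standing in for discharge also keeps its place at Hour 72.
3. As an editorial clarification, add a Day 32 row to Table 8.3-2 or extend the vital-signs rule to laboratory values.

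The cost is SAP wording, one model run with each version of the visit, one derived visit and one table row. It needs no new data and has no alpha implication.
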